### **6.6.3 *Modified Rankin Scale***

The number and percentage of patients in each mRS score category will be reported at the 3 to 6 month and the 12 to 18 month visits by group. For each visit, a Cochran-Mantel-Haenszel “shift” analysis (also known as van Elteren's test, Savitz 2007) will be used to evaluate differences in the mRS distribution between groups. The distribution of mRS

scores is expected to differ by aneurysm status. Analyses will be repeated separately by randomization strata for aneurysm status (recently ruptured vs. not recently ruptured).

Patients with missing mRS data at the 3 to 6 and/or 12 to 18 month visit will have their data imputed via multiple imputation assuming that the data are missing at random. The imputation model will be stratified by randomization assignment and aneurysm status and include age, sex, randomization strata for wide neck status, aneurysm size, and baseline mRS. Since this model includes a mixture of variables types (i.e. continuous, binary and ordinal), a fully conditional specification method will be used (Berglund 2014). Thirty datasets will be imputed and Rubin's methods will be used to combine them and estimate treatment effect (Rubin 1986).

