#### 6.4.3.2 Baseline characteristics

Baseline characteristics will be summarized by randomization assignment using the appropriate descriptive statistics. The specific baseline variables collected include randomization stratification factors, anthropometrics (weight, height), medical history (prior aneurysms treated, smoking status, pre-existing conditions), presenting symptoms, Modified Rankin Scale score, and rupture characteristics (if ruptured, time since rupture at randomization, Fisher Scale, Hunt and Hess scale, WFNS grade, IVH presence, ICH presence, and presence of infarct prior to embolization).

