### **6.8 Multiplicity Adjustment**

Secondary endpoints will provide insights regarding the value of this therapy. The most clinically important secondary endpoints are neurologic morbidity and the mRS scores at the 3 to 6 month visit.

To control type I error across these endpoints we will use a step-wise gate keeping procedure for four hierarchical families of hypotheses, tabled below.

Family	Hypothesis	Description
F1	H1	There is no difference in the risk of angiographic occlusion between randomization groups
F2	H2	There is no difference in the risk of neurologic morbidity between randomization groups
F3	H3	There is no difference in the distribution of mRS at the 3 to 6 month visit
F4	H4	There is no difference in the distribution of mRS at the 3 to 6 month visit within patients with an aneurysm status of recently ruptured
	H5	There is no difference in the distribution of mRS at the 3 to 6 month visit within patients with an aneurysm status of not recently ruptured

The type I error control procedure will be as follows:

1. Test the hypothesis in F1
  - a. If the p-value is greater than or equal to 0.05 stop and conclude no treatment effect
  - b. If the p-value is less than 0.05 proceed to step 2
2. Test the hypothesis in F2
  - a. If the p-value is greater than or equal to 0.05 stop and conclude a treatment effect in F1 only
  - b. If the p-value is less than 0.05 proceed to step 3
3. Test the hypothesis in F3
  - a. If the p-value is greater than or equal to 0.05 stop and conclude a treatment effect in F1 and F2 only
  - b. If the p-value is less than 0.05 proceed to step 4
4. Test the hypotheses in F4 using a 0.05-level Holm-step down procedure. With this procedure, the p-values of both tests are ranked from smallest to largest.
  - a. If the smallest p-value is greater than 0.025, stop and conclude a treatment effect in F1, F2, and F3 only
  - b. If the smallest p-value is less than 0.025 and the largest p-value is greater than 0.05, stop and conclude a treatment effect in F1, F2, F3 and H4 or H5 (whichever had the smallest p-value) only
  - c. If the smallest p-value is less than 0.025 and the largest p-value is less than 0.05, declare a treatment effect across F1, F2, F3 and F4

While other secondary endpoint data will be featured in the publication of the trial, there will be no formal correction of the Type I error rate for multiple testing of statistical hypotheses for any of the other secondary endpoints.

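### The mRS shift test behind H3-H5 names no strata and leaves out baseline mRS, giving up precision that the trial has already collected

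*Combined protocol and SAP*

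**What the plan says.** - **The test.** SAP 6.6.3 specifies a Cochran-Mantel-Haenszel shift analysis at each follow-up visit, "also known as van Elteren's test", which "will be used to evaluate differences in the mRS distribution between groups". No stratification variable is named for the pooled test. The analysis is then repeated within the recently ruptured and not recently ruptured groups.
- **The imputation model.** The same section imputes missing follow-up mRS separately by arm and aneurysm status, from age, "sex, randomization strata for wide neck status, aneurysm size, and baseline mRS".
- **Baseline collection.** The visit schedule in protocol 6.1 marks mRS at screening and enrollment. SAP 6.4.3.2 lists it among the baseline variables: "presenting symptoms, Modified Rankin Scale score, and rupture characteristics".
- **Status of the endpoint.** SAP 6.8 states: "The most clinically important secondary endpoints are neurologic morbidity and the mRS scores at the 3 to 6 month visit". The 3-6 month mRS comparison is H3 in all patients, H4 in recently ruptured and H5 in not recently ruptured patients. H3 is tested only if H1 (occlusion) and H2 (neurologic morbidity) both give p < 0.05. H4 and H5 follow H3 under a Holm procedure. The 12-18 month comparison is outside the hierarchy.

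**The concern.** The SAP treats baseline mRS as informative enough to predict a missing follow-up score, but does not use it when comparing the scores that are observed. Any disability that was present before treatment and persists to follow-up is then part of the noise in the rank comparison.

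Two features of the plan leave the gap open:

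- Van Elteren's test is stratified by construction, but its strata cannot be inferred. Protocol 5.5 lists the randomization strata as rupture status, trial phase and neck type; SAP 3.1.2 lists site, rupture status and neck type.
- The adjustment triggered by baseline imbalance in SAP 6.5.5 covers the primary endpoint only. A chance imbalance in baseline mRS would have no pre-specified remedy in the mRS analysis.

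At stake is the power of three of the five hypotheses under type I error control, and of the 12-18 month comparison.

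**Working it through.** **1. The plan's own figure.** SAP 6.5.2 gives power for the primary endpoint only: 73% versus 82%, 325 per arm, two-sided 0.05, approximately 80% power.

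- Pooled proportion 0.775: √(2 × 0.775 × 0.225) = 0.5906.
- Unpooled: √(0.73 × 0.27 + 0.82 × 0.18) = 0.5871.
- z = (0.09 × √325 − 1.96 × 0.5906) / 0.5871 = 0.792, so power is 78.6%.

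This agrees with the stated figure to within 2 points. Nothing comparable is stated for mRS, so everything below rests on assumed inputs.

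**2. Analytic range.** If the baseline-to-follow-up correlation is ρ, adjustment leaves a fraction 1 − ρ² of the outcome variance. Suppose the adjusted test has 80% power at two-sided 0.05. Then

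power without adjustment = Φ((1.960 + 0.842) × √(1 − ρ²) − 1.960).

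| ρ | Adjusted | Unadjusted | Loss (points) |
|---|---|---|---|
| 0.2 | 80% | 78.4% | 1.6 |
| 0.3 | 80% | 76.2% | 3.8 |
| 0.4 | 80% | 72.8% | 7.2 |
| 0.5 | 80% | 67.9% | 12.1 |

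If instead the planned test is assumed to have 80% power, adjustment raises it to 81.6%, 83.6%, 86.4% and 89.9%. At ρ = 0.4, with adjusted power anywhere from 50% to 90%, the loss is 5.6 to 7.6 points. At 0.025, the first Holm level for H4 and H5, the 80% case loses 1.8 to 13.4 points over the same range of ρ.

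**3. Simulation with the rank test itself.** The formula is a normal approximation, so van Elteren's test was also simulated. Assumptions: 650 patients, half ruptured, assumed mRS distributions, a latent shift of 0.235 SD, and two-sided 0.05 throughout (no Holm levels). Strata were rupture status alone, then rupture status by baseline mRS.

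| Latent correlation (observed within stratum) | H3 | H4 | H5 |
|---|---|---|---|
| 0.4 (about 0.3) | 74.4% to 78.5% | 49.3% to 54.3% | 39.4% to 42.2% |
| 0.5 (about 0.4) | 74.5% to 81.2% | 50.3% to 60.4% | 39.9% to 43.7% |

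The gains are about 4, 5 and 3 points in the first row and about 7, 10 and 4 in the second. At latent correlation 0.2 the H3 gain is only 0.4 points (72.5% to 72.9%).

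**4. Effect of the hierarchy.** H3 needs H1 and H2 to pass first. Take H1 power as 78.6% and assume independent tests. The 7.2-point loss at ρ = 0.4 then becomes, in the overall chance of declaring H3:

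- 7.2 × 0.786 = 5.7 points if H2 always passes;
- 5.7 × 0.5 = 2.8 points if H2 passes half the time;
- 5.7 × 0.05 = 0.3 points if H2 is null.

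The documents give no effect size for H2. The 12-18 month comparison does not pass through these gates.

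**The case against.** The strongest reply is that this is a preference about efficiency. A van Elteren test without baseline mRS is valid under randomization, and using a variable for imputation does not oblige the analyst to test with it: there it makes missing-at-random more plausible, which is a separate purpose. **This stands.** A reader might infer that the planned test is biased or has the wrong type I error. The documents do not support that.

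The reply continues that silence is not exclusion: the strata are unnamed, so baseline mRS is not shown to be ruled out. **This stands as a description.** It does not close the gap, because a confirmatory test with unnamed strata is not fully specified and nothing in 6.6.3 points to baseline mRS as a stratum.

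A reader might also settle on a single loss of about 7 points for H3-H5. That is not a figure from the documents. It needs an assumed correlation near 0.4 and about 80% power, and it does not fit H4 and H5, which use subsets and Holm levels.

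Nor do the documents show that large baseline differences remain within the rupture groups. They give no baseline mRS distribution, and Hunt and Hess grades 4-5 are excluded. They do not say whether baseline mRS in ruptured patients refers to before the rupture or to presentation. If scores in unruptured patients cluster near 0, H5 has little to gain.

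Finally, SAP 6.1 allows an unsuitable method to be replaced before lock. A valid but less efficient test would not obviously trigger that clause.

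**Conclusion.** The point holds as a loss of efficiency and an incomplete specification. Baseline mRS is collected and used to impute the outcome, but the shift test for H3-H5 and for the 12-18 month visit does not include it and names no strata.

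On the assumption that an adjusted test would have 80% power, the loss is about 2 to 12 points for a correlation of 0.2 to 0.5. It varies across H3, H4 and H5, is probably small in unruptured patients if their baseline scores sit near 0, and is diluted for H3-H5 by the requirement that H1 and H2 pass. The true correlation, mRS effect and baseline distribution are unknown from the documents. The change is worth making because it costs almost nothing, not because the planned test is wrong.

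**What to change.** Amend SAP 6.6.3 before data lock, as the SAP's purpose statement permits.

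- **Preferred.** State that the shift test at each visit is stratified by randomized rupture status and baseline mRS category (for example 0, 1, 2, 3, 4-5). For H4 and H5, stratify by baseline mRS category within the rupture group. Fix in advance, blind to arm, a rule for merging sparse categories, such as joining adjacent ones below a stated count with both arms combined. This version leaves out neck status, a randomization stratum, so the SAP should say that this is deliberate.
- **Alternative.** Pre-specify, as the single primary mRS analysis, a proportional-odds model with arm, rupture status, neck status and baseline mRS. This is a different analysis from van Elteren's test and adds a proportional-odds assumption.
- **Either way.** Keep the test without baseline mRS as a sensitivity analysis, with its strata named. State whether baseline mRS in ruptured patients refers to before the rupture or to presentation.

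The cost is a few sentences of SAP text and no new data. The downside is some merging of sparse categories, or one added model assumption.

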### 5.2.2 Clinical Outcome

- Modified Rankin Scale score at the 3 to 6 month and 12 to 18 month visits. The Modified Rankin Scale ranges from 0 (no symptoms) to 6 (dead) (Broderick 2017)

Scale Score	Clinical Outcome
0	No symptoms
1	No significant disability. Able to carry out all usual activities, despite some symptoms
2	Slight disability. Able to look after own affairs without assistance, but unable to carry out all previous activities
3	Moderate disability. Requires some help, but able to walk unassisted
4	Moderately severe disability. Unable to attend to own bodily needs without assistance, and unable to walk unassisted
5	Severe disability. Requires constant nursing care and attention, bedridden, incontinent.
6	Dead

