### **6.6.1 *Neurologic Morbidity***

The number and percentage of patients who experience neurologic morbidity at 24-hours post-operation will be reported by randomization group. The proportion of patients with neurologic morbidity will be compared between groups using a log binomial model and differences between the groups will be summarized using relative risk and the corresponding 95% confidence interval.

Patients that die within 24-hours will be counted as having neurologic morbidity. Survivors missing the 24-hour NIHSS assessment will have their neurologic morbidity outcome imputed via multiple imputation assuming that the data are missing at random. The imputation model will be stratified by randomization assignment and include age, sex, randomization strata for wide neck status, randomization strata for aneurysm status, aneurysm size, and baseline NIHSS. Since this model includes a mixture of variables types (i.e. continuous and binary), a fully conditional specification method will be used (Berglund 2014). Thirty datasets will be imputed and Rubin's methods will be used to combine them and estimate treatment effect (Rubin 1986).

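### SAP 6.6.3 imputes missing mRS scores without separating survivors from deaths, so a patient known to be alive can be imputed as dead

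*Combined protocol and SAP*

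**What the plan says.** SAP 5.2.2 defines the endpoint: "The Modified Rankin Scale ranges from 0 (no symptoms) to 6 (dead". Death is therefore a level of the outcome variable.

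SAP 6.6.3 states who is imputed: "Patients with missing mRS data at the 3 to 6 and/or 12 to 18 month visit will have their data imputed via multiple imputation". The model is run separately by arm and rupture status, and its predictors "include age, sex, randomization strata for wide neck status, aneurysm size, and baseline mRS". Vital status is not listed, and neither is the mRS at the other visit. On method: "Since this model includes a mixture of variables types (i.e. continuous, binary and ordinal), a fully conditional specification method will be used". Thirty datasets are combined by Rubin's rules, and a stratified shift test "will be used to evaluate differences in the mRS distribution between groups".

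SAP 6.6.1 handles the 24-hour endpoint differently. Deaths are settled first: "Patients that die within 24-hours will be counted as having neurologic morbidity". Only then does imputation start, and only for the living: "Survivors missing the 24-hour NIHSS assessment will have their neurologic morbidity outcome imputed via multiple imputation". SAP 6.5.3 likewise says how deaths are treated before the primary endpoint is imputed.

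SAP 6.8 places the 3-6 month mRS in hypotheses H3 to H5. The 12-18 month mRS is analysed in the same way but lies outside that hierarchy.

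**The concern.** A patient who missed the visit but is known to be alive has zero probability of a score of 6. An ordinal model fitted to all observed scores, deaths included, and not conditioned on survival gives that patient a positive probability of 6. Assuming data missing at random does not help, because the fact that rules out a 6 is not in the model. As the predictors are listed, even a patient with a score below 6 recorded at 12-18 months could be imputed as dead at 3-6 months.

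At stake is the completed mRS distribution, above all its worst category. SAP 6.8 counts the 3-6 month mRS among the most clinically important secondary endpoints. Because imputation is done by arm, the false deaths follow each arm's own death share and missingness. They stretch any real difference in deaths, and they create one if missingness differs between arms.

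**Working it through.** The plan states no figure for this step, so there is none to reproduce. Total N = 650 (325 per arm) is from SAP 6.5.2. Mortality and missingness are assumptions, shown as ranges.

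**Formula.** Let D be the deaths, all known and scored 6, and M the known survivors without an mRS. The scores available to the model number N − M, and D of them are 6. If the missing patients receive the average observed share of 6s:

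- false deaths per imputed dataset = M × D / (N − M)
- relative over-count of deaths = M / (N − M)

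With M at 5%, 10% and 20% of all patients, the over-count is 0.05/0.95 = 5.3%, 0.10/0.90 = 11.1% and 0.20/0.80 = 25.0%, whatever the mortality.

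**False deaths per dataset, N = 650**

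| Mortality (deaths) | M = 5% (32.5) | M = 10% (65) | M = 20% (130) |
|---|---|---|---|
| 1% (6.5) | 0.34 | 0.72 | 1.62 |
| 3% (19.5) | 1.03 | 2.17 | 4.88 |
| 5% (32.5) | 1.71 | 3.61 | 8.12 |
| 10% (65) | 3.42 | 7.22 | 16.25 |

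For example, 65 × 32.5 / 585 = 3.61.

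**Base of the percentage.** These figures take M as a share of all patients. If missingness is instead a share m of survivors and mortality is 10%, the over-count is 0.9m/(1 − 0.9m): 0.045/0.955 = 4.7%, 0.09/0.91 = 9.9% and 0.18/0.82 = 22.0% for m = 5%, 10% and 20%.

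**Unequal missingness.** Take 325 per arm and 5% mortality in both (16.25 deaths each), with known survivors without an mRS at 5% of one arm and 20% of the other. Expected 6s after imputation are 16.25/0.95 = 17.1 and 16.25/0.80 = 20.3. The arms did not differ in deaths, but the completed data suggest that they did.

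**Effect on the test.** The stratified shift test was simulated under no treatment effect, with 500 trials per scenario and 30 imputations combined by Rubin's rules. Assumed: 40% recently ruptured; deaths 10% in ruptured and 2% in unruptured; survivors' scores missing completely at random. Imputation was a bootstrap draw from observed scores within arm and rupture stratum, which stands in for the SAP's regression models.

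| Survivors missing (arm 1 / arm 2) | Mean true deaths | Mean false deaths per dataset | Type I error, 0-6 | Type I error, 0-5 for survivors |
|---|---|---|---|---|
| 10% / 10% | 33.8 | 3.4 | 0.052 | 0.050 |
| 20% / 20% | 33.8 | 7.5 | 0.064 | 0.062 |
| 5% / 20% | 33.7 | 4.6 | 0.064 | 0.064 |

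The Monte Carlo standard error is about 0.01. False deaths appear as the formula predicts, but the rejection rate is practically the same under both rules.

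**The case against.** The strongest reply is that section 6.6.3 never says imputed values run from 0 to 6 or that survivors may receive a 6. That range is inferred from silence, and a careful programmer would cap survivors at 5. This is right as far as it goes, and it is why the point is that survivors *can* be imputed as dead, not that they will be. But the section does specify who is imputed, by what method and from which predictors. Following those instructions exactly permits impossible values, and 6.6.1 shows that the SAP draws the distinction where it means to.

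Second, some missing scores belong to patients whose vital status is unknown. SAP 6.6.2 censors those who withdraw or are lost at study exit. For them a 6 is a legitimate draw. This stands: M counts only patients known to be alive, and the documents do not say how many there will be.

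Third, since 6 means dead, a known death could be regarded as already observed. That is the natural reading, but 6.6.3 does not state it.

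Three stronger readings are tempting and not supported:

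- **That H3 to H5 have an inflated false-positive rate.** The simulation does not show this. These hypotheses also concern only the 3-6 month visit and are reached only if H1 and H2 are both rejected.
- **That the reported mRS table must show more deaths than the survival analysis.** Section 6.6.3 does not say whether the category counts use observed or completed data. With observed data there is no mismatch.
- **That the mortality results are compromised.** SAP 6.6.2 analyses observed deaths and does not use the mRS imputation.

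**Conclusion.** The gap is real and worth closing before data lock, but its reach is limited. As written, 6.6.3 allows patients known to be alive to be imputed as dead at either visit. If it is programmed literally, deaths in the completed mRS data are over-counted by about 5%, 11% or 25% when known survivors lacking a score are 5%, 10% or 20% of all patients. At N = 650 this ranges from a fraction of one false death per dataset at 1% mortality to about 16 at 10%.

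These sizes assume that all deaths are known and scored 6, that the missing patients resemble the average observed patient on the model's predictors, and that no cap is applied. If their predictors point to lower risk, there will be fewer false deaths. There are none if no known survivor misses a visit, if nobody dies, or if survivors are capped at 5. The harm is to the completed mRS distribution, its death category and the treatment effect estimated from it. The primary endpoint and the survival analysis are untouched.

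**What to change.** Add to SAP 6.6.3, for both visits:

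1. Every patient known to have died by the visit is scored 6 and is not imputed.
2. For patients known to be alive at the visit, including through a later mRS or other later contact, missing scores are imputed on 0-5 only, from a model fitted to survivors.
3. A 6 may be imputed only when vital status at the visit is unknown.

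The text should also give the date at which vital status is judged, for example the end of the visit window, and say whether the mRS category table uses observed or completed data.

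The cost is a few sentences and a slightly more complex two-step imputation. Nothing new need be collected: death dates are already required for SAP 6.6.2, and fatal events are reported under Protocol 7.2. The SAP's statement of purpose allows revision before data lock.

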## 6. Visit schedule and Assessments

### 6.1 Visit Schedule

	Screening and Enrollment	Embolization Procedure	Discharge	3-6 Month Follow-Up	12-18 Month Follow-Up	Unscheduled Visit(s)
Informed Consent	X					
Inclusion/Exclusion	X					
Randomization	X					
Chart Review	X					
Hunt Hess	X					
Fisher (if applicable)	X					
WFNS (if applicable)	X					
Modified Rankin	X		X	X	X	X
NIHSS			X	X	X	X
Research Data Collection	X	X	X	X	X	X
Clinical Evaluation	X		X	X	X	X
Imaging		X		X	X	X (if indicated)
Embolization		X				
Re-Treat (if applicable)				X	X	X
Evaluate for AEs/SAEs	X	X	X	X	X	X

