#### 3.1.1 Study Duration and Time Points

All patients will be followed for 12 to 18 months post-procedure. Endpoints will be measured at discharge from the index procedure, 3 to 6 months post-procedure, and 12 to 18 months post-procedure. The 3 to 6 month visit and 12 to 18 month visit align with standard of care visits.

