### 6.5.3 *Missing Primary Endpoint Data*

Patients without previous evidence of inadequate angiographic occlusion, either on the 3 to 6 month visit angiogram or on a clinically driven angiogram taken prior to study exit, that miss the 12 to 18 month angiogram, or whose 12 to 18 month angiogram is not readable by the core lab, will be missing the primary endpoint. Patients missing the primary endpoint who die prior to or during the 12 to 18 month visit window (up to 18 months post-randomization) and die with known cause of death related to their aneurysm or unknown cause of death will be considered treatment failures with inadequate occlusion. Patients missing the primary endpoint with a known cause of death unrelated to their aneurysm will be considered missing.

Patients with missing primary endpoint data will have their 12 to 18 month angiographic

occlusion status imputed via multiple imputation assuming that the data are missing at random. The imputation model will be stratified by randomization assignment and include age, sex, randomization strata for aneurysm status, randomization strata for wide neck status, aneurysm size, and angiographic occlusion status at the 3 to 6 month visit. Since this model includes a mixture of variables types (i.e. continuous and binary), a fully conditional specification method will be used (Berglund 2014).

The main feature of the imputation approach is the creation of a set of clinically reasonable imputations for angiographic occlusion for each patient with missing data. This will be accomplished using a set of repeated imputations created by predictive models based on the majority of participants with complete data. The imputation models will reflect uncertainty in the modeling process and inherent variability in patient outcomes, as reflected in the complete data. Thirty datasets will be imputed.

After the imputations are completed, all of the data (complete and imputed) will be combined and the analysis performed for each imputed-and-completed dataset. Rubin's method of multiple (i.e., repeated) imputation will be used to estimate treatment effect (Rubin 1986).

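### The mRS imputation model lists only pre-treatment predictors although discharge mRS and NIHSS are collected, and it does not say whether the two follow-up mRS scores inform each other

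*Combined protocol and SAP*

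**What the plan says.** SAP 6.6.3 sets the rule: "Patients with missing mRS data at the 3 to 6 and/or 12 to 18 month visit will have their data imputed via multiple imputation", assuming missing at random. The model is stratified by arm and aneurysm status. Its listed predictors are age, sex, "randomization strata for wide neck status, aneurysm size, and baseline mRS". It uses fully conditional specification with thirty datasets combined by Rubin's rules.

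Other parts of the documents bear on this list:

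- **Data available.** In the protocol visit schedule (6.1), the "Modified Rankin" row is marked at screening, discharge, both follow-up visits and unscheduled visits. NIHSS is marked at discharge and later. SAP 3.1.1 agrees: "Endpoints will be measured at discharge from the index procedure, 3 to 6 months post-procedure, and 12 to 18 months post-procedure".
- **Reason for missing data.** The text after the exclusion criteria in protocol 4.2 expects death and procedural or disease-related morbidity to leave some patients without follow-up angiography. Protocol 6.2.2 has mRS and NIHSS administered when those angiograms are done.
- **Comparator.** The primary-endpoint imputation model in SAP 6.5.3 does name a post-procedure measurement: "aneurysm size, and angiographic occlusion status at the 3 to 6 month visit".
- **Use of the result.** In SAP 6.8, H3 reads "There is no difference in the distribution of mRS at the 3 to 6 month visit", and H4 and H5 repeat it by rupture status. If H2 is not significant, the rule is "If the p-value is greater than or equal to 0.05 stop and conclude a treatment effect in F1 only".

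**The concern.** Missing at random is a statement about what the imputation model conditions on. Here it conditions on arm, rupture status and pre-treatment variables. Suppose two patients are alike at baseline, one goes home well and the other is discharged severely disabled, and both miss the 3-6 month visit. The listed predictors give both the same imputation distribution. If patients in poor condition miss visits more often, their imputed scores are too good on average. Where the arms truly differ in post-procedure status, the difference is pulled towards zero.

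The 3-6 month mRS carries H3, H4 and H5, three of the five hypotheses in the hierarchy. The discharge scores that would weaken the assumption are already being collected.

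**Working it through.** The documents state no figure to reproduce: they give no missing-mRS rate, no correlation between visits and no expected mRS effect. The check is therefore a comparison of texts followed by an illustration on assumed inputs.

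**Step 1: predictors listed against data scheduled**

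| Measurement | Scheduled (protocol 6.1) | Listed in SAP 6.6.3 |
|---|---|---|
| Baseline mRS | yes | yes |
| Discharge mRS | yes | no |
| Discharge NIHSS | yes | no |
| mRS at the other follow-up visit | yes | not listed; both visits are imputation targets |

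The absence of the discharge scores is plain from the text. The last row is open. In one fully conditional specification model covering both visits, each incomplete score normally predicts the other without being listed as a covariate. SAP 6.6.3 does not say whether the visits are imputed jointly or separately.

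**Step 2: a true difference, same missingness mechanism in both arms**

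Assumptions: standardized mRS; correlation with follow-up of 0.7 for discharge and 0.3 for baseline; 12-16% missing, more often when disabled at discharge; 400,000 per arm, so sampling error is negligible.

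| Scenario | True difference (SD) | Baseline-only model | With discharge added | Shrinkage, baseline-only |
|---|---|---|---|---|
| A | -0.135 | -0.131 | -0.135 | 1 - 0.131/0.135 = 3% |
| B | -0.142 | -0.131 | -0.143 | 1 - 0.131/0.142 = 8% |

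A wider set of assumptions (discharge effect 0.2-0.3 SD, roughly 10-17% missing, moderate dependence) gives about 2-8%. Stronger dependence at 11-21% missing gives about 10-13%.

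An arm mean is off by 0.045 SD in A and 0.081 SD in B, but most of this cancels between arms. The difference is off by 0.135 - 0.131 = 0.004 SD and 0.142 - 0.131 = 0.011 SD. With 325 per arm (SAP 6.5.2), the complete-data standard error is about sqrt(2/325) = 0.078 SD. The bias is then 0.004/0.078 = 0.05 to 0.011/0.078 = 0.14 of a standard error.

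**Step 3: no true difference, trial-sized samples**

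Assumptions: 325 per arm, 30 imputations by arm, Rubin's rules, 400 repeats; correlation with 3-6 month mRS of 0.3 (baseline), 0.7 (discharge) and 0.8 (12-18 month). Each cell shows bias in SD / mean standard error / rejection rate.

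| Missing | Dependence on discharge status | Baseline only | + discharge | + discharge and 12-18 month |
|---|---|---|---|---|
| 10% | same in both arms | -0.005 / 0.0814 / 6.0% | -0.005 / 0.0811 / 6.0% | -0.006 / 0.0800 / 5.0% |
| 20% | same in both arms | 0.000 / 0.0855 / 6.8% | +0.002 / 0.0845 / 5.8% | +0.002 / 0.0820 / 5.8% |
| 10% | one arm only | -0.042 / 0.0817 / 8.3% | +0.010 / 0.0807 / 5.0% | +0.010 / 0.0797 / 4.3% |
| 20% | one arm only | -0.098 / 0.0864 / 20.5% | -0.001 / 0.0839 / 5.2% | -0.002 / 0.0818 / 4.0% |

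Monte Carlo error is about 0.004 SD for bias, about 1 point for rejection rates near 5% and about 2 points near 20%.

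With a common mechanism, the baseline-only standard error exceeds that of the fullest model by 0.0814/0.0800 - 1 = 2% and 0.0855/0.0820 - 1 = 4%. Against the model with discharge alone the excess is 0.0814/0.0811 - 1 = 0.4% and 0.0855/0.0845 - 1 = 1%. So discharge status mainly protects against bias, and most of the precision comes from the other visit's score.

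Both illustrations use normal scores in place of the seven-level mRS and omit age, sex, neck width, aneurysm size and rupture status. They show direction and order of size, not a forecast.

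**The case against.** - **The effect is small and rests on assumed inputs.** This stands. No input to the illustrations comes from the documents, and 0.05-0.14 of a standard error would rarely change a conclusion. Dilution of a real effect is also conservative.
- **H3-H5 may never be tested.** They are reached only if angiographic occlusion and 24-hour neurologic morbidity both give p < 0.05. This limits the stakes. It also means that whenever H3-H5 carry confirmatory weight, the arms have already been found to differ in early neurologic status, which is the setting of step 2 rather than the no-difference setting.
- **Morbidity is named as a reason for missing angiography, not for missing mRS, and protocol 5.2 plans clinical follow-up for everyone.** This is fair. The link runs through protocol 6.2.2, which ties the mRS to the angiogram. It is an inference, though a reasonable one.
- **Extra ordinal predictors may not fit well.** This stands. The model is already split into four arm-by-rupture cells, and the discharge scores may be sparse or collinear in the smaller ones.

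A reader might also infer more than the documents support:

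- *That the SAP leaves out the other visit's mRS.* The text is silent, and a joint model would normally include it. Patients who miss both visits would still gain nothing from it.
- *That deaths will be imputed.* SAP 5.2.2 scores death as 6 and SAP 6.6.3 imputes only missing scores, so a known death is an observed 6.
- *That the planned model leaves 91% of the variance unexplained.* That is 1 - 0.3² = 0.91. It credits baseline mRS alone and ignores the other predictors and the stratification, so it does not describe the planned model.

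**Conclusion.** The point holds as a gap in specification. The mRS imputation model has no listed predictor measured after the procedure, although discharge mRS and NIHSS are scheduled and the protocol itself expects post-procedure morbidity to disrupt follow-up. Whether the two follow-up scores inform each other is unspecified.

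The size cannot be determined from the documents. Under the assumed correlations and a common missingness mechanism, it is a dilution of about 2-8% at 10-17% missing, plus a small loss of precision. It becomes material only if missingness related to discharge status differs by arm: about -0.10 SD and a false-positive rate near 20% at 20% missing, with dependence in one arm only. That is a deliberately unfavourable scenario. Nothing in the documents says it will occur, so it should not be read as the expected error rate for H3-H5.

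No stated figure is wrong and the primary analysis is unaffected. The tests concerned are secondary and conditional. The change is still worth making because it uses scheduled data and removes a dependence on an assumption that is weaker than it needs to be.

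**What to change.** In SAP 6.6.3:

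1. Add discharge mRS as a predictor, and discharge NIHSS as well if the model converges.
2. State that the 3-6 and 12-18 month mRS scores enter one joint fully conditional specification model, each predicting the other.
3. As a clarification only, state that patients known to have died by a visit score 6 and are not imputed.
4. State that convergence and sparse cells will be checked within the arm-by-rupture strata, and how mRS levels will be collapsed if needed.

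The cost is a few sentences and a modest amount of programming. No new data, visits or patients are needed. The SAP's statement of purpose allows revisions before data lock. The one real downside is possible instability in small strata, which item 4 covers.
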